##### **Aims 2 & 3:**

- Primary caretaker(s) of a patient age 25 and under who has been diagnosed

with either CPSD, OTCD, ASD or ALD (broadly defined as those individuals who are responsible for making the child's treatment decisions and who also provide the majority of the child's physical and emotional care)

- Considered, are currently considering, or opted for, liver transplantation as a treatment for UCD.
- Willing to participate in a 60-minute semi-structured interview and/or a 60-90 minute focus group discussion

OR

- Health care provider (e.g. metabolic disease physician, liver transplant surgeon, gastroenterologist, genetic counselor, or nurse) that participates in treating patients diagnosed with either CPSD, OTCD, ASD or ALD,
- Willing to participate in a 60-minute semi-structured interview and/or a 60-90 minute focus group discussion

## 4.2. Exclusion Criteria

### Aim 1:

- Rare and unrelated comorbidities (e.g., Down's syndrome, intraventricular hemorrhage in the newborn period, and extreme prematurity)

### Aim 2 and 3:

- None

## 4.3. Recruitment of Participants

**Aim 1:** De-identified data from the Longitudinal (natural history) Study (LS) of the Urea Cycle Disorders (UCD) will be supplemented with data from subjects identified from two sources: the Studies of Pediatric Liver Transplantation (SPLIT) Research Group and the National Urea Cycle Disorders Foundation (NUCDF).

Longitudinal Study participants will not be recruited to participate in this study, but their data used for this analysis, as is permissible per the LS consent form.

By agreement, when this project is implemented, SPLIT will contact its respective transplant centers to describe the study and its eligibility criteria indicating the number and descriptive characteristics of eligibility based on SPLIT anonymized records asking study staff to contact eligible patients and provide general recruitment materials. NUCDF will also distribute recruitment materials and directly enroll eligible participants to the study. In all cases, interested patients will contact one of the study sites to express their interest in participating in the study.

Enrollment in the UCDC LS will be offered to any patient not already enrolled, so that they can take advantage of the rare disease protocol to capture laboratory data, neurocognitive function and quality of life information, using the resources already in place through the UCDC. Participants interested in enrolling in the LS will be put in

touch with the study coordinator and PI at the nearest (or preferred) UCDC site. The PCORI site coordinator will work closely with LS coordinators to ensure that contact with interested participants is not delayed. We anticipate that a large proportion will agree to participate in the PCORI study, which will require only two visits for neuropsychological testing and self-reported quality of life questionnaire.

**Aim 2 and 3:** UCD patient primary caretakers (typically a parent) will be recruited for interviews and focus groups from NUCDF's outreach to the UCD community and its membership (over 2000 UCD family members) and consented and enrolled by GW staff. We will work collaboratively with NUCDF and Children's National on the content of recruitment materials and means of distributing the materials most effectively, as well as recruiting approximately 40-50% of our primary caretaker interview and focus group sample from families attending NUCDF's Virtual Family Conferences, held annually in July, with a webinar and distribution of recruitment materials and a breakout session for interested families. Additional recruitment will also be conducted on a rolling basis through NUCDF's communication portals, social media site, and discussion boards, and one-on-one outreach, in order to capture families that are unable to attend this conference and thus minimize selection bias. NUCDF has begun to gauge preliminary interest among its membership and has identified approximately 65 families, with varying levels of access to expert care, disease severity, and transplant status, who have expressed interest in participating. NUCDF has established a patient stakeholder research working group, the Patient Powered Research Team (PPRT). Additional families will be invited to participate in the PPRT to expand the representative diversity of the group to meet the aims of the study. Additional recruitment outreach may be conducted on a rolling basis from the pool of patients recruited through SPLIT for Aim 1 of the study.

UCD providers, defined as treating physicians, nurses, and counselors, will be recruited for interviews from a population of approximately 55+ metabolic disease physicians, liver transplant surgeons, gastroenterologists, genetic counselors, and nurses within the 11 U.S. sites participating in the UCDC and additional participating SPLIT sites. GW will work with Children's to reach out to UCDC and SPLIT investigators to request their participation in interviews. NUCDF will identify and refer additional providers (with a focus on liver transplant surgeons) for participation in interviews.

We will use a purposeful sampling strategy (via the NUCDF conference and via the NUCDF communication portals) to recruit a representative sample of 32-48 patient primary caretakers (roughly 20-30% of the available target population) for participation in semi-structured interviews about their experience making treatment decisions for their child with UCD. With the assistance of NUCDF, we will also stratify our sample by 1) access to expert care, 2) disease severity, and 3) transplant status (see section 6.1).

In stage 2 of qualitative data collection, primary caretakers and providers of participants will be asked to take part in focus groups to provide feedback on themes that emerged from our structured interviews and to discuss effective strategies for the dissemination of evidence-based information obtained through this study. Additional patient caretakers will be recruited via NUCDF outreach as described above for participation in these focus

groups until a sample size of 64-80 has been reached. We will conduct 6-8 focus groups with 8-10 participants per group. Additional provider focus groups will be conducted after interviews to further discuss treatment decision making and dissemination strategies.

#### **4.4. Retention Strategies**

**Aim 1:** Since this component comprises only 2 visits for neuropsychological testing, we expect a high retention rate among highly motivated patients referred from and enrolled by NUCDF. In comparison, we have observed ~90% retention in the LS protocol since enrollment began in 2006; the LS is more demanding with regard to laboratory and neuropsychiatric testing. UCD appears to affect equally all ethnic groups, except African American, who are underrepresented (~3%). We will make every effort to enroll African American patients in this study.

**Aim 2:** As this component consists of 60-90 minute interviews and/or participation in focus groups, after which subjects exit the study, retention is anticipated to be near 100% (barring the rare occasion when a participant may voluntarily terminate the interview and/or participation in the focus group).

#### **4.5. Data Elements and Schedule of Events**

##### **Aim 1:**

###### **Baseline Visit**

Confirmation of Eligibility: Once enrolled into the study, the participant's diagnostic testing will be reviewed to assure that the correct UCD diagnosis has been made and eligibility requirements are met based on study inclusion and exclusion criteria.

Baseline Assessment: Historical and new data will be collected at baseline as summarized below. We will use a variety of methods to obtain these data. Certain information will be obtained from a historical review of existing charts and laboratory /treatment data. Careful attention will be paid to accurately note dates for historical information. Other data will be obtained from patients or their families through a standard interview. A Quality of Life survey will also be administered at the baseline visit or afterward by phone or through the RDCRN database. Neuropsychological testing will be performed at the same visit, or at another date.

###### **Historical Data:**

- Eligibility
- Enrollment/demographic information
- Review of past medical records, including:
  - growth charts
  - neurodevelopmental testing
  - neurological evaluation
  - biochemical and diagnostic testing (e.g., ammonia, plasma amino acids, DNA sequencing of UCD genes)

- history of hospitalizations
- medications and other treatments (e.g., dialysis)
- other comorbidities

**Neuropsychological testing and Quality of life questionnaires:**

Neuropsychological tests will be based on age-matched norms for the specific test used (Table 1). These tests overlap with those currently used in the UCDC LS. The findings will be discussed with the participant/parents at the time of the testing, and a report of the results of this testing will be provided to the participant/parent.

Table 1. Validated tests and scales to be used in this study						
Test	Domain	6-35 mo.	3-5 y	6-16 y	≥17 y	Reference
Bayley-II/III	Overall Development (IQ/DQ)	X				[36]
WPPSI-IV			X			[37]
WASI/WASI-II				X	X	[38]
ABAS-II	Adaptive Skills	X	X	X	X	[39]
CBCL	Mood and Behavior		X	X		[40]
BRIEF	Attention/Executive Skills		X	X	X	[41]
TEA-Ch				X		[42]
RCFT				X	X	[43]
TOL-Dx				X	X	[44]
NEPSY	Attention/Executive, Language		X	X		[45]
D-KEFS				X	X	[46]
WRAVMA	Motor		X			[47]
Grooved Pegboard				X	X	
Grip Strength				X	X	[49]
Beery VMI	Visual Motor		X	X		[50]
CVLT-C/II	Learning and Memory		X	X	X	[51]
PedsQL	Quality of Life	X	X	X		[52]
SF-36				X	X	[53]
PROMISE					X	[54-56]

The Quality of Life questionnaires will be administered at the baseline visit to assess the impact the disorder has on the participant's quality of life. Parents of participants aged 1 month to 18 years old will be administered the PedsQL parent-report or parent proxy-report questionnaire. Participants between 13 and 18 years of age will complete the PedsQL child questionnaires for their age group. Adult participants (over 18 years of age) will respond to the SF-36v2 questionnaire and the Patient Reported Outcomes Measurement Information System (PROMIS) questionnaires annually (43, 44). PROMIS questionnaires: Satisfaction with Social Roles and Activities, Cognitive Function (previously called Executive Function), Anxiety, Depression, Emotional/Behavioral Dyscontrol. The site neuropsychologist and/or the site PI will review PROMIS questionnaires within 30 days of administration and follow up with the participant and his/her family, as appropriate, such as if there is any indication that the participant may harm himself/herself or others

**Aim 2 & 3:**

Once referred to the study, primary caretakers (mostly parents) and providers will initially be contacted by the study team to schedule an in person, telephone or video conference interview. Subjects will participate in a single semi-structured interview. Primary caretakers and providers that participate in a semi-structured interview will also be invited to participate in a follow-up focus group. Additional primary caretakers will also be recruited to increase the # of focus group participants and meet our proposed focus group sample size. Focus groups will be conducted during year 2 of the study. As described in detail in section 6.2, data from semi-structure interviews and focus groups will be rendered into codes and subcodes.

## **5. Data and Safety Monitoring Plan**

The study protocol will be reviewed and approved by the National Institutes of Health (NIH) before submission to individual center IRBs for approval. Participant enrollment may only begin with IRB approved consent forms.

This is an observational study that meets the federal definition of minimal risk.

### **5.1. Study Oversight**

The Study Chair has primary oversight responsibility of this clinical trial. The NIH appointed Data (Observational) Safety Monitoring Board (OSMB) has oversight responsibility of the Data Safety Monitoring Plan (DSMP) for this clinical trial. The D/OSMB will review accrual, patterns and frequencies of all adverse events, and protocol compliance every 12 months. The OSMB makes recommendations to the NIH regarding the continuation status of the protocol.

Each site's Principal Investigator and their research team (co-Investigators, research nurses, clinical trial coordinators, and data managers) are responsible for identifying adverse events. Aggregate report- detailed by severity, attribution (expected or unexpected), and relationship to the study drug/study procedures – will be available from the DMCC for site review. Adverse events will be reviewed every 12 months by the research team. A separate report detailing protocol compliance will also be available from the DMCC for a site review on a monthly basis. The research team will then evaluate whether the protocol or informed consent document requires revision based on the reports.

### **5.2. Definitions and Standards**

The Rare Diseases Clinical Research Network defines an adverse event as: "...an unfavorable and unintended sign, symptom or disease associated with a participant's participation in a Rare Diseases Clinical Research Network study."

Serious adverse events include those events that: “result in death; are life-threatening; require inpatient hospitalization or prolongation of existing hospitalization; create persistent or significant disability/incapacity, or a congenital anomaly/birth defects.”

An unexpected adverse event is defined as any adverse experience, the specificity or severity of which is not consistent with the risks of information described in the protocol.

Expected adverse events are those that are identified in the research protocol as having been previously associated with or having the potential to arise as a consequence of participation in the study

All reported adverse events will be classified using the current version of the Common Terminology Criteria for Adverse Events (CTCAE) developed and maintained by CTEP at National Cancer Institute.

Only those events associated with the conduct of the study and as defined above are reportable.

### **5.3. Reporting Timeline**

- Within **24 hours** (of learning of the event), investigators must report any reportable Serious Adverse Event (SAE) that:
  - Is considered life-threatening/disabling or results in death of subject
  - OR-
  - Is Unexpected/Unanticipated
- Investigators must report all other reportable SAEs within **5 working days** (of learning of the event).
- All other (suspected) reportable AEs must be reported to the RDCRN within **20 working days** of the notification of the event or of the site becoming aware of the event.

Local institutional reporting requirements to IRBs, any oversight committee, and the FDA, if appropriate, remain the responsibility of the treating physician and the Study Chair.

### **5.4. RDCRN Adverse Event Data Management System (AEDAMS)**

Upon entry of a serious adverse event, the DMCC created Adverse Event Data Management System (AEDAMS) will immediately notify the Study Chair, site PIs, the Medical Review Officer, and any additional agencies (if applicable- industry sponsor, CTEP, etc) of any reported adverse events via email.

Serious adverse events: The NIH appointed Medical Review Officer (MRO) determines causality (definitely not related, probably not related, possibly related, probably related, definitely related) of the adverse event. The MRO may request further information if necessary and possibly request changes to the protocol or consent form as a consequence of the adverse event. A backup notification system is in place so that any

delays in a review by the MRO beyond a specified period of time are forwarded to a secondary reviewer. The Adverse Event Data Management System (AEDAMS) maintains audit trails and stores data (and data updated) and communication-related to any adverse event in the study.

Non-serious expected adverse events: Except those listed above as immediately reportable, non-serious expected adverse events that are reported to or observed by the investigator or a member of his/her research team will be submitted to the DMCC in a timely fashion (within 20 working days). The events will be presented in tabular form and given to the MRO and RDCRN DSMB on an annual basis. Local site investigators are also required to fulfill all reporting requirements of their local institutions.

The DMCC will post aggregate reports of all reported adverse events for site investigators and IRBs.

## **5.5. Study Discontinuation**

This study will not have study discontinuation rules as it is purely observational as it exercises no control over treatment decisions or their outcomes. The NIH and local IRBs (at their local site) have the authority to stop or suspend this study at any time.

## **5.6. Subject Discontinuation**

An intent to treat approach will be used. All data acquired prior to termination for the reasons outlined below will be included in the primary analysis unless patient withdraws consent. Every effort will be made to conduct a final study visit with the participant and participants will be followed clinically until, if applicable, all adverse events resolve.

- Withdrawal of consent
- Withdrawal by the participant
- Withdrawal by the investigator

## **5.7. Data Quality and Monitoring Measures**

As much as possible, data quality is assessed at the data entry point using intelligent on-line data entry via visual basic designed screen forms. Data element constraints, whether in independent range and/or format limitations or 'relative' referential integrity limitations, can be enforced by all methods employed for data input. QA reports assess data quality post-data entry. As we note, data quality begins with the design of the data collection forms and procedures and incorporates reasonable checks to minimize transcription and omission errors. Of the more important quality assurance measures are the internal validity checks for reasonableness and consistency.

- Data Monitoring: The RDCRN DMCC identifies missing or unclear data and generates a data query to the consortium administrator contact.
- Data Delinquency Tracking: The Data Management and Coordinating Center will monitor data delinquency on an ongoing basis.

## 6. Statistical Considerations

### 6.1. Sample Sizes

**Aim 1.** Of the 185 projected members of the target population, 92 (49.7%) are expected to have received liver transplants and 93 (50.3%) to remain on conservative management. Based on previously published results and characteristics of the UCD patients currently enrolled in our longitudinal study, we expect these groups to be very comparable with respect to UCD severity. As described below, we will use the method of covariate-balanced propensity score matching to create additional groups that are more closely matched on additional severity indicators for the comparative effectiveness analysis. **Table 2** provides a detailed breakdown of the characteristics of study groups.

For **Aims 2 and 3**, we plan to recruit a representative sample of 32-48 patient primary caretakers for participation in semi-structured interviews on their experience making treatment decisions for their child with UCD and an additional 16-48 patient primary caretakers (until a sample of 64-80 is reached) for participation in focus groups to validate information obtained through interviews and to discuss effective dissemination strategies for the evidence-based information obtained through this study.

Table 2. Characteristics of Eligible Transplanted Cases and Comparable Controls										
Group	Total	Type of UCD				Sex M/F	Onset (days)	Peak NH3 (µmol/l)		Surgery Age (mo.)
		CPSD	OTCD	ASD	ALD			# >200, %	Median, IQR	
Transplanted	92	12 (14%)	44 (47%)	22 (24%)	14 (15%)	62/30	2 (1-21)	90 (98%)	958, 938	11.7 (1.5-186)
Conservatively Managed	93	1 (1%)	21 (22%)	37 (39%)	34 (38%)	48/45	3. (1-21)	69 (74%)	403, 781	---

Interview and focus group participants will be stratified by their child's: 1) access to expert care (i.e. yes/no), 2) disease severity (i.e. neonatal onset/post-neonatal onset), and 3) transplant status (pre/no transplant, post-transplant,) (**Tables 3 and 4**). Although not included as an explicit level of stratification, we will also aim to recruit primary caretakers that are diverse in terms of their child's geographic distribution, socioeconomic status, and race/ethnicity.

Table 3. Sample Sizes for Stage 1 Patient Caretaker Interviews				
Disease Severity	Pre/No Transplant			
	Access to Expert Care		Sample Size	
	Yes	No		
Neonatal onset		4-6	4-6	8-12
Post-neonatal onset		4-6	4-6	8-12
Post-Transplant				
Neonatal onset		4-6	4-6	8-12
Post-neonatal onset		4-6	4-6	8-12
TOTAL		16-24	16-24	32-48

Table 4. Sample Sizes for Stage 2 Patient Caretaker Focus Groups				
Disease Severity	Pre/No Transplant			
	Access to Expert Care		Sample Size	
	Yes	No		
Post-Neonatal Onset	Neonatal onset	8-10	8-10	16-20
	Post-neonatal onset	8-10	8-10	16-20
	Post-Transplant			
	Neonatal onset	8-10	8-10	16-20
TOTAL	Post-neonatal onset	8-10	8-10	16-20
		32-40	32-40	64-80

We will also recruit a national cross-section of 25-40 providers from the UCDC and SPLIT sites for participation in semi-structured interviews. Our provider sample will include metabolic disease physicians, liver transplant surgeons, gastroenterologists, genetic counselors, and nurses (**Table 5**).

Table 5. Sample Sizes For Provider Interviews & Focus Groups	
Type of Provider	Sample Size
Metabolic Disease Physician	5-8
Liver Transplant Surgeon	5-8
Gastroenterologist	5-8
Genetic Counselor	5-8
Nurse	5-8
TOTAL	25-40

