**Figure 2. Overall Design of the Study**  
 A randomized controlled trial (RCT) in UCDs is not a feasible option to fill an information gap because of the nature of the alternatives and dearth of affected patients. In the quantitative component of this study (**Aim 1**), we, therefore, propose to implement a natural history observational trial, relying on existing historical and concurrently collected registry data to identify our population of interest. This population consists of patients age 18 and under. Many such patients are already enrolled in a Longitudinal (natural history) Study of Urea Cycle Disorders conducted by the Urea Cycle Disorders Consortium (UCDC). This UCDC study captures data regarding survival, neurocognitive status and quality of life. In order to achieve our target sample size and

broaden our subject population, we intend to merge data from the existing UCDC data set with two additional registries maintained by: 1) the Studies of Pediatric Liver Transplantation (SPLIT) Research Group, housed at the EMMES Corporation and 2) National Urea Cycle Disorders Foundation (NUCDF) patient stakeholders. To study the two UCD patient cohorts, one managed conservatively and the other treated by liver transplantation, we will use covariate balanced propensity score matching to greatly reduce bias in this non-randomized study. Propensity score matching is widely recognized as a best practice alternative when an RCT is not feasible.

In the qualitative component of this study (**Aims 2 and 3**), we intend to enroll a representative sample of pediatric patient caretakers (guided by referrals from the NUCDF) and medical providers, including the treating physician and other clinicians on the team (guided by referrals from UCDC site coordinators) to participate in semi-structured interviews that will explore how decisions about UCD treatment are being made. Patient caretakers will also be asked to take part in focus groups to provide feedback on themes that emerged from the semi-structured interviews and to discuss effective strategies for the dissemination of evidence-based information obtained in this study.

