## 6.2. Analysis Plan

For **Aim 1**, we will use covariate balancing propensity scoring based on the CBPS package in R [28] to create comparable (balanced) groups based on their risk factor (covariate) profile in subjects according to their propensity (probability) to move from conservative management to liver transplantation. This approach leads to a model that predicts treatment assignment (conservative vs. liver transplantation) and balances covariates, especially those related to study outcome(s), and offers the best opportunity to simulate RCT results from observational data. From prior experience, many through the UCDC [26,31,32], we know many of the important risk factors, which include neonatal vs. late onset, number of prior hyperammonemic events, event severity in terms of hyperammonemic coma score [2], ammonia and glutamine levels at regularly scheduled clinic visits, and duration from birth to transplant or index date. In addition to these, we will consider comorbidities, organ function, and other laboratory assessments. The CBPS software will help us choose the model that maximizes covariate balance and generate the CBPS for each participant. The next steps will be to order the dataset according to the CBPS. It is useful at this point to select CBPS to cut points to form homogeneous strata to assess the number of subjects with a liver transplant and conservative management per stratum. Those strata where there are

insufficient numbers (mismatches) of conservative treatment or liver transplant subjects will be described, documented and excluded from the primary analysis due to lack of covariate balance. Before conducting model-based analyses for **Aim 1**, we will compare survival times based on the log-rank test in Kaplan-Meier analysis and the difference between mean scores based on t-tests by treatment for neurodevelopment and quality of life within each stratum to evaluate evidence of heterogeneity. Evidence of heterogeneity will provide clues to interactive effects based on UCD severity which will be modeled in regression analyses below by including a cross products term of treatment type with CBPS. Based on these results, we will develop general linear random effects longitudinal regression models in STATA 14

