[<http://www.stata.com/stata14/>] to perform analysis of covariance that will enable us to evaluate **Aim 1** outcomes of neurodevelopment and quality of life. Each model will include treatment type, the baseline measurement of each outcome, as well as the CBPS and if necessary the cross product of treatment type by CBPS. When we address survival, we will implement Cox Regression models to predict survival time by treatment and will either control for CBPS or stratify on it in the case of heterogeneity.

We used PASS 12 [33] to evaluate statistical power to address study aims for sample sizes per group (liver transplantation vs. conservative management) of 90 and 80 in 2-tailed testing at an alpha of 0.05, which assumes some losses in the sample entering analysis in order to maintain adequate covariate balance between groups. For neurodevelopmental and quality of life assessments, we have 80% power to detect modest 0.4sd effect size differences between groups assuming two repeated measurements per person correlated at 70% (ICC). For mortality, assuming the rate in the conservatively treated group remains about 28%, the study will have 80% power to detect and increase in the liver transplant group of about 60% which is robust to differences in sample size between 80 and 90 per group. The study is well powered to detect any clinically meaningful difference in neurocognitive outcomes and QOL and adequately powered to detect a moderate difference in mortality between groups.

For **Aim 2**, interview data will be managed using QSR International NVivo 10 software [[http://www.qsrinternational.com/products\\_nvivo.asp](http://www.qsrinternational.com/products_nvivo.asp)], a program that allows us to collect, organize, and code qualitative data sources. Although not explicitly a grounded theory study, our approach to the analysis of primary caretaker and provider interview data will borrow from aspects of Strauss and Corbin's systematic procedures for grounded theory work [34]. No existing framework or theory currently exists that describes the process which UCD patients and their families undertake when making the difficult decision to pursue liver transplant or continue conservative management. Thus, some of Strauss and Corbin's analysis techniques are suitable for this study aim, which seeks to describe a process/experience in a field where there is little pre-existing evidence.

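### Sections 4 and 6.1 promise a propensity-matched Aim 1 comparison, section 6.2 describes a stratified, trimmed and score-adjusted one, and no method is named as primary

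*Combined protocol and SAP*

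**What the plan says.** Two sections of the combined protocol and SAP name matching.

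- Section 4, in the text on overall design: "we will use covariate balanced propensity score matching to greatly reduce bias in this non-randomized study".
- Section 6.1, Aim 1: "As described below, we will use the method of covariate-balanced propensity score matching to create additional groups that are more closely matched". It says these groups serve the comparative effectiveness analysis.

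Section 6.2 describes a different sequence for Aim 1:

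1. Estimate the CBPS, order the children by it, and "select CBPS to cut points to form homogeneous strata to assess the number of subjects with a liver transplant and conservative management per stratum".
2. Strata with too few children on one treatment are "excluded from the primary analysis due to lack of covariate balance".
3. Within each remaining stratum, compare survival by log-rank test, and neurodevelopment and quality of life by t-test, to look for heterogeneity.
4. In the light of those results, build random-effects regressions for neurodevelopment and quality of life: "Each model will include treatment type, the baseline measurement of each outcome, as well as the CBPS". A treatment-by-CBPS product is added if thought necessary.
5. For survival, fit Cox models that "will either control for CBPS or stratify on it in the case of heterogeneity".

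The synopsis mentions only CBPS used to form balanced groups. Section 5.6 also uses the term primary analysis, but to say that data collected before a participant leaves the study are kept.

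**The concern.** Matching, trimming by strata and adjusting for the score need not analyse the same children. A matched comparison keeps only children with a close counterpart. Trimming keeps everyone in a stratum that has enough of both treatments. Adjustment uses all retained children and assumes a form for the relation between score and outcome. The analyses differ in precision and can estimate different average effects.

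Table 2 suggests that the retained sets could differ substantially. The groups are far apart on CPSD (12 transplanted v 1 conservatively managed), OTCD (44 v 21), peak ammonia above 200 µmol/l (98% v 74%) and median peak ammonia (958 v 403 µmol/l).

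Section 6.2 also leaves steps open that touch the outcome data. Treatment groups are compared on outcome within strata before the final model is set. Those results then inform whether the product term enters and whether the Cox model adjusts or stratifies, with no stated decision rule. The cut points and the number that counts as insufficient are not given either. The study is meant to inform families choosing between the two treatments, so its answer should not depend on which section the analyst follows.

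**Working it through.** **1. The sections side by side.** Section 6.1 points forward for a description of matching. Section 6.2 gives no pairs, ratio, caliper, algorithm or matched-set analysis. The conflict is in the text and needs no calculation.

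**2. The plan's own power figure.** Section 6.2 gives 80% power for 0.4 SD with 90 and 80 per group, two-sided alpha 0.05, and two measurements per child with ICC 0.70.

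- SD of the mean of two measurements = √((1 + 0.70)/2) = 0.922.
- Power = Φ(0.4 / (0.922 × √(1/n₁ + 1/n₂)) − 1.96).
- 90 v 80: 0.4/0.1417 − 1.96 = 0.864, power 80.6%.
- 80 per group: 78.3%. 90 per group: 82.9%.

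The figure reproduces. It allows for losing only 185 − 180 = 5 to 185 − 160 = 25 children.

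**3. Illustration of what matching could cost.** The documents give no matched sample size. Assume 1:1 pairs that must share a UCD type. This is my assumption: section 3.3.4 asks that the specific disorder be taken into account, but 6.2 does not list type among its named risk factors. From Table 2, the maximum number of pairs is

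min(12,1) + min(44,21) + min(22,37) + min(14,34) = 1 + 21 + 22 + 14 = 58.

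With 58 per group: 0.4/(0.922 × √(2/58)) − 1.96 = 0.376, power 64.7%. The difference detectable with 80% power is 0.48 SD.

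This uses the plan's own variance. If baseline adjustment with correlation 0.7 is credited instead, the SD is √(1 − 0.49) = 0.714. Power is then 85.5% at 58 per group, against 95.4% at 90 v 80. The loss from matching remains, but power stays above 80%.

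**4. How often the verdicts differ, with a true 0.4 effect.** All inputs beyond Table 2 are assumed.

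| Simulation | Pair compared | Opposite verdicts at 0.05 |
|---|---|---|
| Nested sets, 85 and 58 per group (70 per group) | larger v smaller set | 20.3% (12.2%) |
| 185 children on Table 2's mix, logistic score, caliper 0.2 SD, quintiles dropped below 5 per group | matched v score-adjusted | 19.2–22.0% |
| Similar design, calipers 0.1/0.2/0.5 SD, two ammonia spreads | matched v score-adjusted | 20–25% |
| Same as the row above | stratified v score-adjusted | about 5% |

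In the second simulation, matching kept about 48 pairs and trimming kept about 145 children. Its rejection rates for stratified and score-adjusted analyses were 69.4 v 68.9%, 62.8 v 69.4%, 70.4 v 75.7% and 76.6 v 80.0%. Two tests must disagree at least as often as their rejection rates differ, so the largest gap sets a floor of 69.4 − 62.8 = 6.6% in that scenario. The last row is therefore approximate, but well below the matched comparison.

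**5. With no true effect.** The chance that at least one analysis is significant was 7.8% for the nested sets of 85 and 58. It was 5.5–8% for matching plus score adjustment, and 7.0–9.2% for all three methods in the second simulation.

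**The case against.** The strongest reply is that section 6.2 governs. Section 6.1 defers to it, the synopsis speaks only of balanced groups, and 6.2 itself uses the word mismatches for strata short of one treatment: "insufficient numbers (mismatches) of conservative treatment or liver transplant subjects will be described, documented and excluded from the primary analysis". On this view, matching is a loose label for balancing within score strata. The planned sizes of 80 to 90 per group fit light trimming better than pair matching. Section 6.2 also identifies which strata the primary analysis leaves out, gives one model family for neurodevelopment and quality of life, and runs the within-stratum tests as diagnostics. Most of this stands.

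A reader might therefore infer too much in three ways:

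- That the plan offers three rival primary analyses. It does not. Stratification as an estimator appears only for survival, and matching is never specified.
- That the false-positive rate is above 5%. The 7–9% figures apply only if someone picks the method after seeing results, and the plan does not say that will happen.
- That the survival conclusion has been shown to turn on the choice. Survival was not simulated. The Table 2-based simulations used one outcome per child without baseline adjustment, which is simpler than the planned models.

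The reply does not remove the conflict in wording, the undefined cut points and threshold, or the outcome-informed model choice within 6.2.

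**Conclusion.** The point holds as an inconsistency with an open model choice, not as an arithmetic error. Two sections promise a method that the analysis section does not contain, and no method is named as primary. Section 6.2 most likely governs. If it does, disagreement between its own approaches is small, about 5% in one set of assumed simulations and at least 6.6% in one scenario of another. If the promise of matching were taken literally, the consequences are larger: at most 58 pairs and about 65% power under exact matching on UCD type and the plan's own variance, and opposite verdicts in about 20% of studies with a true 0.4 SD effect. These sizes rest on the stated assumptions, and the textual conflict does not. It should be corrected, because the choice changes which children are analysed and can change the conclusion.

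**What to change.** - In 6.2, name one primary contrast per outcome in the retained strata: the treatment effect from the CBPS-adjusted random-effects analysis of covariance for neurodevelopment and for quality of life, and one Cox form, chosen in advance, for survival.
- Fix the score model, the cut points and the minimum number per treatment in a stratum before any outcome is compared by treatment.
- Make the heterogeneity tests and the treatment-by-CBPS term secondary. If the term stays in the primary model, centre the CBPS or average over its distribution. Otherwise the treatment coefficient is the effect at a score of zero, not an overall effect.
- Replace the references to matching in sections 4 and 6.1 with this description, and align the use of primary analysis in 5.6.
- Label any matched comparison as a sensitivity analysis that cannot replace the primary result.

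This costs wording in four sections and no extra children or data. The price is that neither a matched comparison nor a model chosen from the outcome results can supply the main finding.
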